At the time of writing and to our knowledge this will be the first study to assess whether a group psychological intervention is effective using a standardised therapeutic manual adapted to those diagnosed with GID. Moreover, it looks at whether delivering psychological interventions in an online format in a group setting is acceptable and feasible with this patient population and in the NHS environment. Outcomes from this study will not only shape future psychological interventions but also promote psychological support for this cohort of patients who have expressed wanting this service. If group interventions are proven to be effective, it will mean that patients may have more rapid access to psychological intervention rather than inevitable long waiting lists for individualised psychological support. In addition, the group intervention can be adapted for further gastrointestinal conditions in the future.

2. Project Team

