To assess the effectiveness, feasibility and acceptability of an online ACT based psychological intervention on psychological measures (distress, psychological flexibility, QOL and medical outcomes (described below in section 6) when compared to a control group who will receive treatment as usual (TAU).

4.2 Secondary Objective:

The study aims to recruit people with a diagnosis of GID, with a description of the results of those with CIPO against those non-CIPO to see whether the effectiveness or needs differ between these two groups.

5. Study Design

This study will be a pilot randomised controlled trial (RCT) with patients diagnosed with gastrointestinal dysmotility. Assessment of QoL of intestinal failure (IF) patients is very complex as IF is not only affected by the HPN treatment itself but also by the underlying disease and frequency of hospital readmissions. Therefore, a range of data will be collected including demographic characteristics, psychological outcomes, and medical outcomes, collected at different timepoints to allow for analysis (further detail is provided section 7.6 below).

Blinding of investigators or participants will not be possible in this study as participants and investigators will know whether participants had been allocated to the group or not. Participants allocated to the group intervention will be put into a group of 9-10 people. There will be maximum five rounds of the group intervention over the study period to meet sample size. The intervention is adapted from the Better Living with Illness group protocol [22] based on ACT. The group will be delivered over 7 weeks in weekly two-hour sessions, with a follow up 'reunion' at 8 weeks. A treatment manual has been adapted by the chief investigator who has received specialist training in ACT and previous experience of running this intervention online to people with long-term conditions. Each session utilises experiential exercises and metaphors to cover core ACT processes. Worksheets and guided mindfulness meditation exercises will be recommended to facilitate learning and encourage home practice. The intervention also covers problem solving skills, pacing, assertiveness skills and goal setting as they are important features of living with a long-term condition such as GID. An overview of the content of group sessions is provided in figure 1.

Figure 1, Session content of group

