6.8 Outcome measurement

Several outcome measures and data will be collected:

- Demographic characteristics and background information such as: age, sex, marital status, ethnicity, employment, diagnosis, duration of diagnosis and previous psychology input. This will be gathered by asking participants to complete a brief questionnaire once they have consented to take part in the study.
- Psychological outcomes collected through multiple pseudonymised self-reported questionnaire:
 - Generalised Anxiety Disorder Assessment (GAD-7) [23] to assess anxiety
 - Patient Health Questionnaire (PHQ-9) [24] to assess depression
 - Acceptance and Action Questionnaire (AAQ-II) [25] to assess psychological flexibility.
 - The RAND 36-item Health Survey 1.0 (SF-36) [26] to assess health-related quality of life (HRQoL).

These items will be measured at baseline (T1/pre-treatment); session 7 (T2/post treatment), and 8 weeks follow-up (T3/2-month follow-up).

- Medical outcomes:
 - Gastrointestinal/ HPN complications

- HPN requirements
- Hospital readmissions
- Opioid use
- Anti-depressant use

Medical outcomes will be collected accessing medical records at baseline and post follow up

A feedback evaluation questionnaire will also be used to measure the feasibility and acceptability of ACT intervention.

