7.5 Stopping rules

Although no adverse events are anticipated, and it is not anticipated that the study will be stopped prior to its intended end-date. However, the study will be halted if:

- New information comes to light which means that the aims of the study are futile
- Safety issues come to light regarding the intervention
- Resources to conduct the study are no longer available
- Abuse of group guidelines, group guidelines include but are not exclusive to; remaining confidential, try to refrain from using mobiles, showing respect, listening and contributing where it feels comfortable to do so, joining from a secure space where participants will not be disturbed and participants will also be offered the opportunity to have telephone check ins where they can raise any concerns about any of the above or if anything else arises. Clinical judgements will also be made.
- If the study fails to recruit less than 10% of invited participants after 6 months of recruitment

8. Record keeping and data management

All information obtained from study participants will be treated as confidential and will comply with the requirements of the General Data Protection Regulations 2018 and the NHS Code of Confidentiality. All data collected will be stored on a secured (password protected) database with access available only to the chief investigator and study team responsible for handling and processing the relevant data. Any personal identifiable information will be stored separately from any interview content to ensure it remains anonymous. Study participants will never be identified by name when data or information are published or presented in the future.

9. Statistical analyses and data handling

Quantitative analysis

Descriptive statistics will be included for all psychological and medical outcomes. Further analysis is summarised in the table:

Objective	Method to measure this
Acceptability	The percentage of all patients randomised to the intervention arm minus deaths that complete the 2-month follow up. This will be compared to the percentage of controls (minus deaths) that complete the 2-month follow up. Completion will be defined as attendance at least 3 out of the 8 sessions. True completion will be defined as the number of participants who completed the whole intervention (all 8 sessions).
Feasibility	For those in the intervention group only: The results of the feedback evaluation questionnaire given after every intervention session.

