Effectiveness	
The preliminary effect of the intervention will be estimated using the estimated mean difference between trial arms at post-treatment and 2 months follow up, adjusted for baseline scores, from analysis of covariance (ANCOVA). The analysis will be conducted using Stata 14 and an alpha level of 5%. This will be completed for all psychometric measures.
 
Results of the subgroup analysis will be described, comparing those with Chronic intestinal pseudo-obstruction (CIPO) against those non-CIPO to see whether the effectiveness or needs differ between these two groups.

---------------	---

Qualitative analysis

Qualitative interview audio recordings will be transcribed verbatim and all identifying information will be removed. Data will be analysed using reflexive thematic analysis [27-29]. Thematic analysis will include data familiarisation, initial coding, and sub-theme formation, and theme labelling.

10. Dissemination of Results and Publications

The final outcomes from the study will be communicated via presentations in scientific meetings and by peer reviewed publications. We will aim to publish the results approximately 12 months after completion of the study. The study and results may be promoted and publicised more widely via the Sponsor Trust's Research & Innovation website and on the PORT charities website.

11. References

4. Di Lorenzo, C., & Youssef, N. N. (2010, February). Diagnosis and management of intestinal motility disorders. In *Seminars in pediatric surgery* (Vol. 19, No. 1, pp. 50-58). WB Saunders.

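### Section 9 sets a 5% alpha for every psychometric score at two time points with no lead estimate, and gives the medical outcomes in objective 4.1 no between-arm estimate

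*Protocol*

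**What the plan says.** **Objective.** The single primary objective, in protocol section 4.1, reads: "To assess the effectiveness, feasibility and acceptability of an online ACT based psychological intervention on psychological measures (distress, psychological flexibility, QOL and medical outcomes", judged against a control group on treatment as usual (TAU). The study summary in section 1 also sets medical outcomes against that control group.

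**Outcomes.** Section 6.8 lists four questionnaires (GAD-7, PHQ-9, AAQ-II, SF-36), taken at baseline (T1), post-treatment (T2) and 8-week follow-up (T3). It also lists five medical outcomes: gastrointestinal/HPN complications, HPN requirements, readmissions, opioid use and antidepressant use. For these it says: "Medical outcomes will be collected accessing medical records at baseline and post follow up". No outcome is ranked above another.

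**Analysis.** Section 9 opens with "Descriptive statistics will be included for all psychological and medical outcomes". The Effectiveness row then uses ANCOVA for the "estimated mean difference between trial arms at post-treatment and 2 months follow up, adjusted for baseline scores". It continues "The analysis will be conducted using Stata 14 and an alpha level of 5"%, and closes with "This will be completed for all psychometric measures". The same row calls the effect preliminary. The table's other two rows cover acceptability and feasibility.

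**The concern.** Two parts of the primary objective do not fit the analysis written for it.

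First, the plan fixes a significance level for every score at both times, under an objective worded as effectiveness, and names no score or time that matters most. Several results will be available, and nothing in the protocol says which one a reader should look at. The scores are self-reported and section 5 says blinding is not possible, so choosing the lead after the data are seen would be hard to defend. A 5% alpha also sits badly beside a pilot whose effect is called preliminary.

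Second, the medical outcomes belong to the primary objective and are to be set against TAU, yet the only analysis that compares outcome scores between arms is limited to psychometric measures. At stake is whether that part of the objective yields an effect estimate with its uncertainty, or only summary tables whose layout is not stated.

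**Working it through.** **Inputs from the protocol**
- Alpha: 5% (section 9, Effectiveness row). Sidedness is not stated; two-sided is assumed. No adjustment is stated.
- Measures: 4, for example "Generalised Anxiety Disorder Assessment (GAD-7) [23] to assess anxiety" (section 6.8).
- Between-arm time points: 2 (section 9).
- SF-36 scores to be analysed: not stated. One score is taken here, which gives the smallest count.

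**Step 1. The plan's own figure.** For one test, 1 − (1 − 0.05)^1 = 0.05, which is the stated 5%. The protocol gives no sample-size or power figure, so there is nothing else to reproduce.

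**Step 2. Number of tests.** 4 measures × 2 time points = 8.

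**Step 3. Independent tests, no true effect.**
- Expected number of false positives: 8 × 0.05 = 0.4.
- Chance of at least one: 1 − 0.95^8 = 1 − 0.6634 = 0.3366, or 33.7%.

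**Step 4. Correlated tests.** The scores will be correlated, so 33.7% is too high for this setting. The protocol gives no correlations, so a range was assumed. Eight normal test statistics were simulated (200,000 draws per case). The correlation between different measures at different times was the product of the two correlations shown.

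| Correlation between measures | 0.5 over time | 0.7 over time |
|---|---|---|
| 0.3 | 29.7% | 27.6% |
| 0.5 | 27.0% | 24.8% |
| 0.7 | 22.6% | 20.9% |

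The range is about 21% to 30%.

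**Step 5. With one named lead.** One score at one time point gives 5.0%. Changing from p-values to 95% intervals does not achieve this alone: the chance that at least one of eight intervals excludes zero is the same as in steps 3 and 4. The lead has to be named as well.

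**Step 6. Medical outcomes, section against section.**

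| Place | What it provides |
|---|---|
| 4.1 | Medical outcomes are part of the primary objective, against TAU |
| 6.8 | Five medical outcomes, from records at baseline and after follow-up |
| 9, opening sentence | Descriptive statistics; by-arm presentation not stated |
| 9, Effectiveness row | ANCOVA between arms, psychometric measures only |
| 9, other rows | Acceptability and feasibility only |

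No line of section 9 defines a between-arm estimate for any of the five. Readmissions and complications are events that accumulate over time, so an estimate for them also needs a counting period.

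**The case against.** The strongest reply is that this is a pilot and the Effectiveness row is about estimation. It sets no decision rule, and the 5% may only fix the confidence level. Multiplicity handling and SF-36 scoring can sit in a statistical analysis plan that is not shown. Describing sparse medical events by arm is a normal choice in a pilot.

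Much of this stands. Nothing in the protocol says that one significant score establishes effectiveness, so the percentages describe what could happen if results were read that way. The absence of a multiplicity method is not the complaint. What remains is text the protocol does fix: an alpha applied to every score, an effectiveness objective with no lead outcome, and a primary objective that goes further than its analysis.

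Three stronger readings are tempting but unsupported:
- A reader might take "If group interventions are proven to be effective" in section 1 as a claim this trial intends to make. It is a conditional remark about future services.
- A reader might count eight SF-36 scales, giving 11 scores × 2 times = 22 tests and 1 − 0.95^22 = 67.6%. The protocol does not say the scales will be tested separately. More SF-36 scores would raise the error, but 8 tests is the count to cite.
- A reader might infer that unequal periods before and after baseline bias the readmission and complication results. The protocol gives no look-back length, and the same periods in both randomised arms would not bias the between-arm comparison. They could mislead only a before-after table within an arm.

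**Conclusion.** The point holds in two limited parts.

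1. Section 9 applies a 5% alpha to at least 8 comparisons with no lead, in a trial that calls its effect preliminary. The chance of at least one false positive is 33.7% under independence and about 21% to 30% under the assumed correlations. These figures assume one score per measure, two-sided tests and no true effect on any score.
2. The medical part of objective 4.1 has no defined between-arm estimate. This follows from the text and rests on no assumption. A reader might go further and infer that the medical question cannot be answered at all. That is too strong, because descriptive results could be tabulated by arm, although the protocol does not say so.

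Neither part invalidates the trial. Both should be corrected before the data are seen.

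**What to change.** - **Section 9, Effectiveness row.** Replace the 5% alpha with baseline-adjusted between-arm differences and 95% confidence intervals for every score at both times. State that they are preliminary and that no claim of effectiveness will rest on significance.
- **Lead estimate.** Name one score and one time point in advance as the lead estimate. This orders the reporting; it does not bring back a test.
- **Medical outcomes, one of two routes.** Either add to section 9 a between-arm estimate with 95% confidence interval for each medical outcome, adjusted for baseline where available, and define in section 6.8 one counting period from baseline, the same in both arms, for readmissions and complications. Or reword objective 4.1 so that medical outcomes are described by arm only.

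The cost is rewording sections 9 and 6.8 (or 4.1) and a little more analysis. No new visits or questionnaires are needed, and the record review after follow-up is already planned, though it must capture events over the defined period. The trial gives up significance claims on individual scores.

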7.4 Study progress reports.....	13
7.5 Stopping rules	14
8. Record keeping and data management.....	14
9. Statistical analyses and data handling	14
10. Dissemination of Results and Publications	15

1. Study Summary

To assess the effectiveness, feasibility and acceptability of an Acceptance and Commitment Therapy (ACT) based psychological intervention delivered in a group format by a qualified psychologist on psychological measures (distress, psychological flexibility, Health-related Quality of Life (HRQOL)), and medical outcomes (described in section 6) when compared to a control group who will receive treatment as usual (TAU) within a patient group with a diagnosis of Gastrointestinal Dysmotility (GID). A further description of the results of those with Chronic intestinal pseudo-obstruction (CIPO) against those non-CIPO will also be included to see whether the preliminary effectiveness or needs differ between these two groups.

The ACT intervention will be carried out in an online format and consist of 7 weekly sessions followed by an 8-week follow up with each session lasting approximately 120 minutes. An online format will be utilised due to the logistics – an online format will allow all participants to attend, taking into consideration the COVID pandemic and geographical location of patients in our service being a national centre for patients needing home parenteral nutrition (HPN). All patients will be followed up and asked to complete feedback forms after each session to assess effective components of the intervention. A subset of patients will also be invited to take part in a qualitative interview based on their experiences of the intervention. Patient experts from the Pseudo Obstruction Research Trust (PORT) and our patient focus group will be invited to be involved in aspects of the study such as the study design, development of the therapeutic manual, recruitment, and dissemination of the study's results.

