2.4 Organisational Structure and Responsibilities

Chief Investigator:

Design and conduct of study
Preparation of protocol and revisions
Recruitment of participants
Organising study meetings
Reviewing progress of the study and agreeing to changes in the protocol if necessary
Oversight of patient safety by conducting regular meetings with study team
Publication of study reports
Study budget holder
Responsible for data management plan

Sub-investigator:

- Design and conduct of study
- Preparation of protocol and revisions
- Recruitment of participants
- Organising study meetings
- Reviewing progress of the study and agreeing to changes in the protocol if necessary
- Oversight of patient safety by conducting regular meetings with study team
- Publication of study reports
- Study budget holder
- Responsible for data management plan

3. Background Information and Rationale

Gastrointestinal dysmotility (GID) has no universally accepted definition but it is a broad term that encompasses a spectrum of disorders where there is dysregulation or disruption of the complex enteric neuromuscular co-ordination necessary for motility of food through the gastrointestinal tract [1, 2]. At the severe end of the spectrum, disruption to GID can lead to intractable gastrointestinal symptoms (pain, cramps, bloating, difficulty maintaining weight, constipation, diarrhoea, nausea, vomiting, malnutrition) [1,2], and is a recognised cause of people needing long term home intravenous feeding, known as home parenteral nutrition (HPN) [1-6]. GID can be separated into sub-types of Chronic intestinal pseudo-obstruction (CIPO) and non-CIPO; the latter is characterised by symptoms representative of intestinal occlusion despite no physical obstruction being present. A study found that the CIPO sub-type of GID is associated with higher HPN dependency, higher incidence of bacterial overgrowth and more surgical intervention compared to those with a non-CIPO sub-type of GID [7].

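### The secondary objective asks whether effectiveness differs between CIPO and non-CIPO, but the plan only describes subgroup results and names no estimate of that difference

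*Protocol*

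**What the plan says.** The subtype question appears in three places in the protocol, each time with description as the method.

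- Section 1 (Study Summary) promises a further description of results by subtype "to see whether the preliminary effectiveness or needs differ between these two groups".
- Section 4.2, the only secondary objective, plans to recruit people with gastrointestinal dysmotility (GID) "with a description of the results of those with CIPO against those non-CIPO to see whether the effectiveness or needs differ".
- Section 9, Effectiveness row: "Results of the subgroup analysis will be described, comparing those with Chronic intestinal pseudo-obstruction (CIPO) against those non-CIPO", for the same stated purpose.

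The same row names a model for the overall comparison. It is an ANCOVA giving the mean difference between arms at post-treatment and at 2 months, adjusted for the baseline score, for all psychometric measures, at a 5% alpha. No subtype term, difference between subgroup effects or interval for such a difference is mentioned.

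Section 3 (Background) introduces the subtypes: "GID can be separated into sub-types of Chronic intestinal pseudo-obstruction (CIPO) and non-CIPO; the latter is characterised by symptoms representative of intestinal occlusion", and the sentence ends "despite no physical obstruction being present".

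**The concern.** The objective has two halves. Whether *needs* differ by subtype can be answered by describing the two groups. Whether *effectiveness* differs cannot. It is a question about the difference between two between-arm differences, and the plan names a method for the overall arm comparison only.

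A reader given one treatment effect for CIPO and another for non-CIPO will compare them by eye. With small subgroups the two will usually look different whether or not the true effects are. Without an interval for the difference, nothing in the report says how much of the gap is noise. The objective invites exactly that comparison.

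**Working it through.** **No figure to reproduce.** The protocol gives no sample size, standard deviation, target effect or CIPO share. The calculation below only illustrates how precise the missing estimate would be.

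**Inputs**

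- Size: section 5 allows at most five rounds of 9 to 10 people. So 5 × 9 = 45 to 5 × 10 = 50 in the intervention arm. This is a ceiling inferred from the rounds, not a planned sample size.
- Allocation 1:1 (assumed; section 6.1 gives no ratio).
- Correlation r between baseline and follow-up score: 0.5 (assumed), with 0 to 0.7 as a range.
- CIPO share p: 20 to 50% (assumed), the same in both arms.
- Two-sided 5% (sidedness is not stated). No dropout and no clustering by therapy group. Effects in SD units.

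**Formulas**, with n per arm:

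- Overall effect: SE_main = √[(2/n)(1 − r²)]
- Arm-by-subtype interaction: SE_int = √[(1 − r²)(2/(np) + 2/(n(1 − p)))] = SE_main / √[p(1 − p)]
- 95% half-width = 1.96 × SE

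**Overall effect, r = 0.5**

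- n = 45: √(0.0444 × 0.75) = 0.183, half-width 0.36 SD
- n = 50: √(0.0400 × 0.75) = 0.173, half-width 0.34 SD

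**Interaction, r = 0.5**

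| CIPO share | SE_int / SE_main | Half-width, n = 45 | Half-width, n = 50 |
|---|---|---|---|
| 50% | 1/√0.25 = 2.00 | 0.72 SD | 0.68 SD |
| 30% | 1/√0.21 = 2.18 | 0.78 SD | 0.74 SD |
| 20% | 1/√0.16 = 2.50 | 0.90 SD | 0.85 SD |

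Over r = 0 to 0.7 the interaction half-width runs from 0.56 SD (n = 50, r = 0.7, share 50%) to 1.03 SD (n = 45, r = 0, share 20%).

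**Power, for scale only.** Using Φ(0.5/SE_int − 1.96) at r = 0.5, power to detect a 0.5 SD difference between the subtype effects is Φ(0.5/0.456 − 1.96) = 0.19 at the low end (n = 45, share 20%). At the high end (n = 50, share 50%) it is Φ(0.5/0.346 − 1.96) = 0.30. The interaction is therefore worth reporting as an estimate with an interval, not as a test.

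**The wording in section 3.** The sentence names CIPO first and non-CIPO second, so its pronoun points to non-CIPO. The description that follows, occlusive symptoms without a physical obstruction, is what the term pseudo-obstruction itself says. The sentence therefore conflicts with the name it explains.

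**The case against.** The strongest defence is that description suits a pilot. Section 1 speaks only of preliminary effectiveness, and section 9 calls even the main result preliminary. Model terms for an exploratory subgroup are often left to a statistical analysis plan. That plan is not at hand and may contain the interaction, and nothing in section 9 forbids it. This stands in part and keeps the point modest. But the protocol is not silent. It names description as the method in three places and gives a verdict on differing effectiveness as its purpose.

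A second objection is that the remedy will not answer the question either, because the interval will be wide. That is true. The gain is that the report then states the uncertainty.

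A third is that replacing description outright would lose the half of the objective about needs. That is right, so the description should stay for that half.

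Two stronger readings are tempting, and the document does not support them.

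- A reader might infer that the plan will often declare a false subtype difference. If the true effect were 0.5 SD in both subtypes, exactly one subgroup would reach p < 0.05 in about 50 to 55% of trials (45 to 50 per arm, r = 0.5, CIPO share 30 to 50%). That figure presumes a separate significance verdict in each subgroup. The protocol plans no such rule: the 5% alpha is stated for the ANCOVA between arms, and the subgroup results are only to be described.
- A reader might infer that the slip in section 3 would swap the subgroup labels and reverse the secondary conclusion. It sits in background narrative, nothing in the protocol classifies patients from it, and the term carries its own meaning. The next sentence uses CIPO by name without confusion.

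**Conclusion.** The point holds as a modest, low-cost improvement. For the effectiveness half of the only secondary objective, the stated method does not produce the quantity asked about. The missing quantity is the arm-by-subtype difference, with a standard error 2.0 to 2.5 times that of the overall effect for CIPO shares of 50% down to 20%. At 45 to 50 per arm and r = 0.5, the 95% interval is about ±0.7 to ±0.9 SD. These figures rest on assumed inputs and on a ceiling for arm size. Fewer participants or dropout would widen the interval.

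The needs half of the objective is adequately served by description. The section 3 wording is a clerical error with no demonstrated effect on the analysis.

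**What to change.** In the Effectiveness row of section 9, keep the descriptive comparison for needs and add, for effectiveness:

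*The difference in treatment effect between CIPO and non-CIPO will be estimated as the arm-by-subtype interaction in the same baseline-adjusted ANCOVA and reported with its 95% confidence interval as an exploratory result. Both subgroup effects will be taken from this model. No claim of differing effectiveness will be based on separate subgroup results.*

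The cost is two extra coefficients (subtype and its interaction with arm) in a model already planned, and three sentences. With four instruments at two time points this gives at least 4 × 2 = 8 interaction intervals, a further reason for the exploratory label. The downside is that the intervals will be wide and will show that the pilot cannot separate the subtypes.

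As an editorial correction, reword the sentence in section 3 so that the description of occlusive symptoms without physical obstruction agrees with the term pseudo-obstruction.
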